#### **10.5.2.2 COVID-19 Ordinal Outcomes Scale**

The percentage of subjects at each clinical status using NIAID ordinal scale at Days 7, 14, and 28 will be analyzed.

1. Death

---

2. Hospitalized, on invasive mechanical ventilation or extracorporeal membrane oxygenation (ECMO)
3. Hospitalized, on non-invasive ventilation or high flow oxygen devices
4. Hospitalized, requiring supplemental oxygen
5. Hospitalized, not requiring supplemental oxygen - requiring ongoing medical care (COVID-19-related or other medical conditions preventing hospital discharge)
6. Hospitalized, not requiring supplemental oxygen - no longer requires ongoing medical care
7. Not hospitalized, limitation on activities and/or requiring home oxygen
8. Not hospitalized, no limitations on activities

Mean value by treatment group will be plotted over time.

Comparison of the mean worst daily NIAID ordinal scale values by Days 7, 14, and 28. The worst ordinal scale will be fitted by a proportional odds model with treatment, age, sex, baseline severity and number of risk factors as covariates.

In addition, proportion of subjects worsening from baseline will be presented, where worsening is defined as the proportion of subjects with any worsening on the NIAID ordinal scale from baseline to Days 7, 14, and 28.

The following events (observed at any time point during the study treatment period) will be summarized:

- Proportion of subjects hospitalized
- Duration of hospitalization (DOH; in days)
- Proportion (percentage) of subjects admitted to ICU

All hospitalization events will be listed.

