4.10.3 Secondary Efficacy Variables

Hospitalization Percentage

Hospitalization percentage is defined as the percentage of subjects who experience any of the following events due to all causes by Day 28:

- Hospitalization for \geq 24 hours or
- Supplemental oxygen for \geq 24 hours in response to $\text{SpO}_2 \leq 93\%$ or
- Death

The same process used for the primary endpoint analysis will be used to compare the difference between treatment groups.

The following sensitivity analysis for hospitalization percentage will be performed among subset of mITT subjects:

- With dosing days > 7 days;
- With one or several major risk factors below:
 - Single risk factor: age (≥ 50 years; ≥ 60 years), major underlying medical conditions (overweight, obesity, hypertension, diabetes, smoking);
 - Combination of age factor in column 1 and other major underlying medical conditions in column 2 in the table below (e.g., age ≥ 50 years and/or obesity at randomization; age ≥ 60 years and/or obesity at randomization);

Age	Major underlying medical conditions
≥ 50 years	Overweight
≥ 60 years	Obesity Hypertension Diabetes Smoking

- With aged ≥ 50 years and days from symptom onset to study randomization ≤ 5 days and days from the positive SARS-CoV-2 Prior to first dosing ≤ 3 days;
- With aged ≥ 50 years and higher than normal biomarkers (CRP, Ferritin, D-dimer).

All sensitivity analyses will be conducted using one-sided CMH chi-square tests used for the primary endpoint analysis. Forest plots for the sensitivity analysis will be presented.

Change from Baseline to Days 3, 7, 14 and 28 in SARS CoV-2 Viral Load

Change of SARS-CoV-2 viral load from baseline, which will be evaluated in log base 10 scale, will be summarized, and plotted by treatment group and listed. Two sample t-tests will be used to compare differences in the change of SARS-CoV-2 viral load between treatment groups at Day 3, 7, 14 and 28, respectively.

Also, an analysis of covariance (ANCOVA) model will be used to compare the change from baseline in SARS-CoV-2 viral load at Day 3 with fixed effects for treatment group, age and stratification factors (sex, race and ethnicity, and number of risk factors), and baseline viral load as a covariate. If systematic pattern is identified from the residual of predicted values, a transformation of the baseline viral load will be employed to improve the performance of the model. Estimated treatment differences

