Time to sustained 100% SARS-CoV-2 viral reduction (in days) is defined as:

Date when sustained 100% SARS CoV-2 viral reduction is changed to 'Yes' - first dosing date + 1.

If a patient has not experienced SARS-CoV-2 clearance by completion or early discontinuation of study/study treatment, the patient will be censored at the date of their last visit during the post-treatment period.

Time to sustained 100% SARS CoV-2 viral reduction and will be summarized and plotted by treatment group with mITT set using the Kaplan-Meier (KM) method. The 2-sided 95% CIs for the 25th, 50th and 75th percentiles, as well as at days 3, 7, 14 and 28 using the Brookmeyer and Crowley method will be reported when estimable. P-value will be obtained from the log-rank test stratified by age, and sex, race and ethnicity, and number of risk factors at randomization. Hazard ratios and corresponding 95% confidence intervals will be obtained from a Cox proportional hazard model which treated treatment group as a unique covariate, and age, and sex, race and ethnicity, and number

of risk factors as stratas. The Cox proportional hazard model will be also performed by subgroup of duration since symptom onset to randomization category (≤ 3 days; > 3 days).

SARS CoV-2 Viral Clearance

SARS-CoV-2 Viral clearance (Yes/No) is defined when at least two consecutive negative tests proceed a positive test with all tests ≥ 24 hours apart. The date of viral clearance is defined as the earliest date between the consecutive negative tests.

The proportion of subjects that achieve SARS-CoV-2 clearance at Days 3, 7, 14, and 28 will be summarized by treatment in frequency tables, plotted and listed. Viral clearance can only be achieved (Yes) at days with a negative result. Generalized estimating equation (GEE) model will be used to model the proportions of achieving SARS-CoV-2 clearance at different visits. The model will consider treatment group, visit, treatment-by-visit interaction, age and stratification factors (sex, race and ethnicity, and number of risk factors) as fixed effects, and subject as a random effect. Comparisons of GT0918 to placebo for odds ratios (ORs), corresponding 95% CIs and p-values will be calculated at each visit.

Time to SARS-CoV-2 Clearance

Time to SARS-CoV-2 clearance (in days) is defined as:

Date when SARS-CoV-2 clearance status is changed to 'Yes' - first dosing date + 1.

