- Comparison of the proportion of NIAID ordinal scale by Days 3, 7, 14, and 28: ordinal generalized estimating equation (GEE) with treatment, age, stratification factors (sex, race and ethnicity, and number of risk factors), visit, and interaction of visit and treatment will be included in the model as fixed effects, and subject will be included as a random effect. Odds ratios with 95% confidence intervals and p-values will be presented. If data are too sparse for one level of the above factors, the factor will not be included in the statistical model/test to avoid convergence issue. Inferential analysis will only be performed if data warrants.
- Proportion of subjects worsening from baseline (worsening is defined as any worsening on the NIAID ordinal scale from baseline to Days 3, 7, 14, and 28)

Stacked bar plot by treatment group and visits at Day 1, 3, 7, 14 and 28 will be produced for NIAID ordinal scale. Also, mean value by treatment group will be plotted over time.

All NIAID ordinal scales through the study period will be listed in listing.

Other Analysis for Clinical Status

Below summaries for other analysis for clinical status will be provided as well:

- Summary of Hospitalization and Extended Care Facility Admissions by Day 28 (COVID-19 related will be summarized separately)
Note: Hospitalization (≥ 24 hours) includes: Hospitalization, Emergency room and ICU. Extended Care Facility Admittance is excluded.
 - Number and proportion of subjects hospitalized
 - Duration of Hospitalization
 - Number and proportion of subjects hospitalized by admission type: Hospitalization, Emergency Room, Intensive Care Unit (ICU) and Extended Care Facility
 - Duration by admission type
 - Comparisons of proportion of hospitalization between treatment group will be made using FIRTH logistic regression, with adjusting age and the stratification factors (sex, race and ethnicity, and number of risk factors). Odds ratios with 95% confidence intervals and p-values will be present. If data are too sparse for one level of the above factors, the factor will not be included in the statistical model/test to avoid convergence issue. Inferential analysis will only be performed if data warrants.
- Summary of New Oxygen Use by Day 28 (COVID-19 related will be summarized separately)
 - Number and proportion of subjects requiring any oxygen use
- Summary of COVID-19 Related Medical Attended Visits by Day 28
 - Proportion of subjects with COVID-19 related medical attended visits

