
All hospitalization events and COVID-19 related medical attended visits will be listed.

Time to Hospitalization

Time to Hospitalization (in days) is defined as:

First hospital admission date - first dosing date + 1.

Note: Hospitalization (≥ 24 hours) includes Hospitalization, Emergency room and ICU. Extended Care Facility Admittance is excluded.

The following two summaries will be generated separately:

- All-Cause Hospitalization
- COVID-19 Related Hospitalization

If a patient has not experienced hospitalization by completion or early discontinuation of study/study treatment, the patient will be censored at the date of their last visit during the post-treatment period.

Time to hospitalization will be evaluated up to Day 28 and will be summarized and plotted by treatment group with mITT set using the Kaplan-Meier (KM) method. The 2-sided 95% CIs for the 25th, 50th and 75th percentiles, as well as at days 3, 7, 14 and 28 using the Brookmeyer and Crowley method will be reported when estimable. P-value will be obtained from the log-rank test stratified by age, and sex, race and ethnicity, and number of risk factors at randomization. Hazard ratios and corresponding 95% confidence intervals will be obtained from a Cox proportional hazard model which treated treatment group as a unique covariate, and age, and sex, race and ethnicity, and number of risk factors as stratas. The Cox proportional hazard model will be also performed by subgroup of duration since symptom onset to randomization category (≤ 3 days; > 3 days).

If cases of hospitalization are too sparse (e.g., < 1 case in one treatment group), no time to hospitalization analyses will be performed.

Proportion of Symptom Resolution

All symptom resolution is defined as

all symptoms (those scored 0-3*) on the symptom questionnaire scored as absent (scored 0), with each symptom resolution absent for at least 48 hours.

Note: * Seven individual questions from COVID-19-Related Symptom Questionnaire are included here: questions 3, 4, 5, 6, 7, 8 and 9.

Additionally, all symptom resolution will be defined differently to include all individual questions scored 0-3 and related outputs will be noted as sensitivity analysis. It is defined as

all symptoms (those scored 0-3*) on the symptom questionnaire scored as absent (scored 0), with each symptom resolution absent for at least 48 hours.

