Note: * Nine individual questions from COVID-19-Related Symptom Questionnaire are included here: questions 1 through 9.

The proportion of subjects with all symptom resolution will be performed at Days 3, 7, 14, and 28 by treatment in frequency tables and listed using mITT set. Generalized estimating equation (GEE) model will be fitted with the response of symptom resolution mapped to categories of Yes or No and with treatment, age, stratification factors (sex, race and ethnicity, and number of risk factors), time

effect and time*treatment interaction terms included in the model as covariates. Odds ratios with 95% confidence intervals and p-values will be present.

Total symptom score (seven individual questions from COVID-19-Related Symptom Questionnaire included here are questions 3, 4, 5, 6, 7, 8 and 9) and change from baseline in total symptom score to Days 3, 7, 11, 14 and 28 will be summarized by treatment group. Change from baseline will be compared using mixed model repeated measures (MMRM) with the fixed effects of baseline total symptom score, age and stratification factors (sex, race and ethnicity, and number of risk factors) and the random effect of subjects and with time effect and time*treatment interaction terms included in the model. Change from baseline in total symptom score will also be graphically displayed.

Additionally, total symptom score will be calculated differently to include nine individual questions (1 through 9) and related outputs will be noted as sensitivity analysis.

A summary of overall COVID-19 related symptoms, including overall symptoms severity, overall general physical health and returned to usual physical health, at Days 3, 7, 11, 14 and 28 will be provided in frequency table and listed.

Additionally, the proportion of subjects with at least 2 points decrease in symptom score (total of ratings) from baseline to Days 3, 7, 14 and 28 will be summarized and listed as well. Generalized estimating equation (GEE) model will be fitted with the response of at least 2 points decrease mapped to categories of Yes or No and with treatment, age, stratification factors (sex, race and ethnicity, and number of risk factors), time effect and time*treatment interaction terms included in the model as covariates. Odds ratios with 95% confidence intervals and p-values will be present.

Time to All Symptom Resolution

Time to all symptom resolution (in days) is defined as:

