First date when all symptom resolution status is changed to 'Yes' - first dosing date + 1.

If a patient has not experienced symptom resolution by completion or early discontinuation of study/study treatment, the patient will be censored at the date of their last visit during the post-treatment period.

Time to all symptom resolution will be applying the same KM methods and Cox proportional hazard models introduced in the time to hospitalization section.

Symptom Improvement

Symptom improvement is defined as a change in severity of overall symptoms * from a higher score to a lower score, which is defined as following:

symptoms scored as moderate or severe at baseline are scored as mild or absent,
OR

symptoms scored as mild or absent at baseline are scored as absent.

Note: * The overall symptoms question (overall question 1) under overall COVID-19 related symptoms from COVID-19-Related Symptom Questionnaire is included here.

Additionally, symptom improvement will be defined by individual symptom questions from symptom questionnaire as below and related outputs will be noted as sensitivity analysis. It is defined as a patient experiencing both:

symptoms * scored as moderate or severe at baseline are subsequently scored as mild or absent,

AND

symptoms * scored as mild or absent at baseline are subsequently scored as absent.

Note: * Seven individual questions from COVID-19-Related Symptom Questionnaire are included here: questions 3, 4, 5, 6, 7, 8 and 9.

The proportion of subjects with symptom improvement at Days 3, 7, 11, 14 and 28 will be summarized by treatment in frequency tables and listed using mITT set. Generalized estimating equation (GEE) model is fitted with the response of symptom improvement mapped to categories of Yes or No and with treatment, age, stratification factors (sex, race and ethnicity, and number of risk factors), time effect and time*treatment interaction terms included in the model as covariates. Odds ratios with 95% confidence intervals and p-values will be present.

Time to Symptom Improvement

Time to symptom improvement (in days) is defined as:

Date when symptom improvement status is changed to 'Yes' - first dosing date + 1.

If a patient has not experienced symptom improvement by completion or early discontinuation of study/study treatment, the patient will be censored at the date of their last visit during the post-treatment period.

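### The secondary GEE and Cox models for viral clearance, viral reduction and symptom response omit the baseline value of the outcome; they stay valid but give up power

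*SAP*

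**What the plan says.** All of the models concerned are in SAP 4.10.3.

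- **Viral GEEs** (sustained 100% reduction; clearance): "The model will consider treatment group, visit, treatment-by-visit interaction, age and stratification factors". Subject is then listed as a random effect.
- **Symptom resolution GEE**: "fitted with the response of symptom resolution mapped to categories of Yes or No and with treatment, age, stratification factors", plus time and its interaction with treatment. The GEE for a decrease of at least 2 points has the same terms.
- **Symptom improvement GEE**: "fitted with the response of symptom improvement mapped to categories of Yes or No and with treatment, age, stratification factors", again plus time and its interaction with treatment.
- **NIAID scale**: "ordinal generalized estimating equation (GEE) with treatment, age, stratification factors", with visit, visit by treatment, and subject as a random effect.
- **Cox models** for times to viral reduction, clearance, symptom resolution and symptom improvement: "Cox proportional hazard model which treated treatment group as a unique covariate", stratified by age, sex, race and ethnicity, and number of risk factors.

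The same section treats continuous outcomes differently. The Day 3 viral-load ANCOVA has the listed factors "and baseline viral load as a covariate", the viral-load MMRM also adjusts for baseline load, and the symptom-score MMRM adjusts for baseline total score.

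The baseline data exist. Protocol 7.2.8 schedules a viral load before the first dose. SAP 4.2 defines baseline and gives a fallback for the questionnaire and ordinal scale when screening and first dose fall on the same day.

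**The concern.** Being virus-negative or symptom-free on a given day is likely to depend on where the subject started. For some of these endpoints the starting value limits the outcome by definition:

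- A subject whose baseline total is 0 or 1 cannot fall by 2 points.
- Resolution uses questions 3 to 9 only, whereas entry requires one symptom, with reference to the 14-item list in Protocol Appendix 2. A subject with only nasal, throat, gastrointestinal or smell and taste symptoms can start at zero on all seven items.
- Improvement asks for a different step from a moderate or severe baseline than from a mild one.

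Leaving out a prognostic baseline value costs power and leaves any chance difference between the arms in the estimate. The section already makes this adjustment for the continuous versions of the same measures, and no reason is given for the difference.

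**Working it through.** **Figures in the plan.** The only sample-size statement (SAP 4.12: 668 subjects, about 90% power, one-sided 0.025, 97% versus 91%) concerns the primary endpoint. It reproduces: a fixed design needs 328 per arm (656). With the O'Brien-Fleming-type interim at half the information, 90% power needs about 661 (pooled variance) or 650 (unpooled), and power at 668 is 90.3% to 90.8%. No response rate, effect size or baseline association is given for the secondary models, so everything below rests on assumptions.

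**Assumptions.** One visit; 334 per arm (668 at 1:1); marginal response 50% versus 60%; two-sided 0.05; a standardised baseline covariate with log-odds slope g per SD; 4,000 simulated trials per setting; logistic model with and without the covariate. Here z = mean log-OR / mean SE, and power is approximately Φ(z − 1.96).

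| g | Unadjusted log-OR / SE = z | Adjusted log-OR / SE = z | Simulated power, unadjusted → adjusted | Gain (points) |
|---|---|---|---|---|
| 0 | 0.410 / 0.157 = 2.61 | 0.411 / 0.157 = 2.62 | 74.0% → 74.4% | 0.4 |
| 0.5 | 0.407 / 0.157 = 2.59 | 0.431 / 0.162 = 2.66 | 73.3% → 76.1% | 2.9 |
| 1.0 | 0.410 / 0.157 = 2.61 | 0.497 / 0.173 = 2.87 | 74.2% → 82.3% | 8.1 |
| 1.5 | 0.409 / 0.157 = 2.61 | 0.579 / 0.188 = 3.08 | 74.4% → 87.2% | 12.8 |

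Check at g = 1: Φ(2.61 − 1.96) = Φ(0.65) ≈ 74% and Φ(2.87 − 1.96) = Φ(0.91) ≈ 82%, in agreement with the simulation. The Monte Carlo error of a single power figure is about √(0.74 × 0.26 / 4000) = 0.7 points.

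The adjusted SE is larger, not smaller. Power rises because the conditional log-OR moves further from zero than the SE grows.

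**Type I error.** With 50% in both arms, the two-sided rejection rate was 4.7% to 5.3% unadjusted and 4.8% to 5.0% adjusted.

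**Chance imbalance.** The standardised baseline difference between arms has SD √(2/334) = 0.077, so 95% of trials lie within ±1.96 × 0.077 = ±0.15. At g = 1, the edge of that range shifts the treatment log-odds by about 0.15 on the conditional scale, roughly one unadjusted SE (0.157). A one-SD imbalance shifts it by 0.077, about half an SE.

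**NIAID.** Subjects enter as outpatients not needing supplemental oxygen, so the baseline score is in practice 7 or 8. As a stand-in, take a two-level baseline (assumed 70/30 split), a binary response of 50% versus 62%, and baseline log-ORs of 0.5, 1.0 and 1.5. Power moves from 87.0% to 88.1%, 87.0% to 89.2%, and 87.6% to 91.3%: a gain of about 1 to 4 points.

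**Limits.** The simulation leaves out age and the stratification factors. If these are correlated with baseline, the extra gain is smaller. No Cox model was simulated.

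**The case against.** The strongest reply is that nothing here is an error. Randomisation protects the tests without baseline adjustment, the models already adjust for age and three stratification factors, and the Cox analyses are repeated by symptom duration. One more covariate is then a choice about efficiency, and its benefit cannot be sized from the documents. All of that stands, and it sets the weight of the point.

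Several stronger readings are tempting but not supported:

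- **Bias or invalidity.** A reader might infer that the estimates are systematically biased. They are not: the imbalance is chance imbalance and is already reflected in the unadjusted SE.
- **Loss of precision.** A reader might expect a smaller SE after adjustment. For a log odds ratio the SE rises, and the gain is in power.
- **A NIAID baseline term removed by the SAP.** The protocol model in 10.5.2.2 was a "proportional odds model with treatment, age, sex, baseline severity and number of risk factors as covariates", but it was fitted to the worst score by each day, whereas the SAP has a repeated-visit GEE. Baseline severity is the mild/moderate category (SAP 4.10.1.3), not the NIAID score, and Protocol 10.1 lets the SAP supersede. No ANCOVA or MMRM is planned for NIAID, so the contrast within the section does not apply there. The SAP also drops factors when data are sparse.
- **A different odds ratio through the random effect.** With a subject SD of 1 to 2 on the logit scale, the marginal log-OR is 1/√(1 + 0.346 × SD²) = 0.86 to 0.65 of the subject-specific one. That matters only if someone fitted a mixed model despite the named GEE. The phrase is most naturally loose wording for the clustering unit, and it needs a wording correction.

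The reply does not explain why a baseline that is collected, and used for the continuous form of the same measure, is left out of the response and time-to-event form.

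**Conclusion.** The omission is confirmed for the viral-reduction, clearance, symptom-resolution, 2-point-decrease and symptom-improvement GEEs, and for the Cox models of the four corresponding times. The planned analyses are valid. The cost is lost power: none if baseline is not prognostic, and about 3, 8 and 13 points at assumed slopes of 0.5, 1.0 and 1.5 per SD (single-visit logistic model, 334 per arm, 50% versus 60%). Chance imbalance also goes unadjusted. For NIAID the expected gain is small. The gain for the Cox models was not quantified.

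These are secondary comparisons, and SAP 4.10.1.2 describes type I error control only for the interim look at the primary endpoint. The primary CMH analysis is not touched. The change is worth making because it is cheap, but the plan does not fail without it.

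**What to change.** Before unblinding, amend SAP 4.10.3 as follows.

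1. **Viral GEE and Cox models:** add baseline log10 viral load, with a stated convention for values below the LoQ (59.9 copies/mL).
2. **Symptom resolution (GEE and Cox) and 2-point decrease:** add the baseline total of the items used in that endpoint, so the nine-item sensitivity version takes the nine-item baseline.
3. **Symptom improvement:** add baseline overall question 1 to the main GEE and Cox models, because the main definition rests on that question and not on a total score. Add the seven-item baseline total to the seven-item sensitivity version.
4. **NIAID ordinal GEE:** add the baseline score or the protocol's baseline severity, if the data permit.
5. **Target of estimation:** state that the adjusted odds or hazard ratio is conditional on baseline as well as on age and the stratification factors.
6. **GEE wording:** in the viral-reduction, clearance and NIAID models, replace subject as a random effect with repeated measures within subject, a named working correlation and robust standard errors.

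The cost is SAP text and one extra term per model, with no new data. Subjects without a baseline value drop out of the adjusted models, so report their number by arm.
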